# 3 Background/Rationale & Purpose

# 3.1 Background Information

Vitamin D deficiency has been a worldwide health problem for over a century, now affecting over 1 billion people on this planet. Although technology is drastically advancing, we still are unable to put an end to this health emergency.

Vitamin D can be introduced in the body in two ways, 1) via diet and 2) through the sun. Few foods naturally contain vitamin D (either  $D_2$  or  $D_3$ ) such as oily fish. For instance fresh wild salmon (3.5oz or

100g) has between 600-1000 IU of vitamin D3. Canned tuna (3.6oz or 102 g) has about 230 IU of vitamin D3. Sun-dried mushrooms and egg yolks are also viable sources of vitamin D. Sun-dried shiitake mushrooms have about 1600 IU of vitamin D2 whereas egg yolks have about 20 IU of vitamin D2 or vitamin D3. There are some fortified foods that also contain vitamin D; fortified milk and fortified orange juice each has about 100 IU/8 oz of vitamin D3. Some cereals, such as Quaker Oatmeal has as much as 40 IU vitamin D/cup. Margarine has about 60 IU of vitamin D/tablespoon. In a study that looked at the plasma levels of 25(OH)D3 amongst fish eaters and non-fish eaters (vegans and vegetarians), those who did not consume fish had lower levels of 25(OH)D3 in both the summer months (20%) and winter months (38%). Thus the consumption of fish in the diet is critical in maintaining vitamin D status throughout the year, especially during the winter months.

When assessing the optimal dietary intake of vitamin D, there might be some controversy as to which guideline to follow. The Institute of Medicine (IOM) issued guidelines to maintain adequate serum 25(OH)D levels above 20 ng/mL. The Endocrine Society's guidelines reflect the needs to treat and prevent vitamin D deficiency and maintain a 25(OH)D status above 30 ng/mL. One would have to consume a significant amount of fish and fortified food products to meet the above recommendations. Thus, it is critical that we incorporate sun exposure into our everyday lives, and/or take vitamin D supplements.

When ultraviolet B (UVB) radiation (wavelength of 290-320 nm) from the sun is absorbed into the skin, it converts 7-DHC, which is predominantly located in the stratum spinosum and stratum basale, to previtamin  $D_3$  which is thermodynamically unstable. Over several hours it isomerizes into vitamin  $D_3$ . The vitamin  $D_3$  from the skin and the vitamin  $D_2$  from food and supplements enters the circulation and are hydroxylated in the liver by a 25-hydroxylase to become 25-hydroxyvitaminD (25(OH)D), which is the major circulating form of vitamin D. 25(OH)D is hydroxylated again in the kidneys by 1alphahydroxylase to become 1,25-dihydroxyvitamin D (1,25(OH)2D), which is the active form of vitamin D. When calcium levels are too high, 24-hydroxylase activity increases, hydroxylating C24 and making, 24,25-Dihydroxyvitamin D (24,25(OH)2D) and 1,24,25-trihydroxyvitamin D (1,24,25-(OH)3D). This step begins the process of the degradation of both metabolites into inactive water-soluble metabolites that can be excreted in the bile. The ability to maintain 25(OH)D levels via sun exposure is influenced by the zenith angle of the sun. The zenith angle is defined as the oblique angle between the sun's rays and the earth's surface. The time of day, season, and latitude on the earth's surface all affect the zenith angle. Above 37° latitude during the months of November through February, there is a significant decrease in the amount of UVB photons hitting the earth's surface, as much as 80%-100% depending on latitude . Thus, for those living in areas at a zenith angle incompatible for producing vitamin D in the winter, they need to obtain their vitamin D via supplements and/or food containing or fortified with vitamin D.

Those living above 37° latitude during the months of November through February could also rely on artificial UVB light sources such as the Sperti lamp or UVB emitting LEDs. These lights permit the skin to convert 7-dehydrocholesterol into vitamin D allowing the body to maintain adequate vitamin D levels while avoiding exposure to the sun. In particular, these lights are resourceful to those having fat

malabsorption disorders such as Crohn's disease, cystic fibrosis, and/or gastric bypass. For these individuals who are unable to absorb vitamin D from the diet, exposure to UVB is the primary way of maintaining an adequate vitamin D status.

UVB phototherapy is a potential solution to the problem. Importantly, narrowband UVB (NB-UVB) phototherapy can be safely used. Long-term studies to date do not indicate a significantly increased risk of skin cancer in an age- and sex-matched control population who have not received UVB phototherapy.  In a 2005 literature review, a search from 1966 to June 2002 was conducted. Eleven studies involving about 3400 subjects (including those with >300 lifetime treatments) were included. Except for 1 Finnish study, all studies showed no increased skin cancer risk with UVB phototherapy. In a 2012 systematic literature review examining NB-UVB and risk of skin cancer, four studies followed a total of 6,385 subjects. None of the four studies found an increased risk of skin cancer in psoriasis subjects treated with NBUVB.  The above studies were mostly in Caucasians with skin types I-III. In a 2011 study of 445 Koreans (skin type III-V) treated with NB-UVB, no melanoma cases were reported within the mean follow-up period of 34.4 months. The investigators also concluded that there were no statistically significant differences in non-melanoma skin cancer between the NB-UVB and control groups. In the largest study on the safety of vitiligo treatment ever conducted, a 2020 retrospective cohort enrolled 60,321 subjects with vitiligo.  Subjects were classified into 5 groups: 0 sessions of NB-UVB; 1-49 sessions; 50-99 sessions; 100-199 sessions; and ≥200 sessions. 717 subjects had at least 500 phototherapy sessions. The risk of nonmelanoma skin cancer did not increase with increasing total sessions of NB-UVB. Further, the subjects who had at least 500 sessions of NB-UVB phototherapy had no greater risk of skin cancer than the subjects who did not undergo NB-UVB phototherapy at all.

Solius has created The Solius Photobiologic System (SPS), which is an experiential device that allows a user to receive a calibrated and calculated dose of vitamin D using wavelengths of UV light that facilitate the body's endogenous production of vitamin D and a variety of biologically controlled feedback mechanisms. The output of SPS is very similar to a NB-UVB device, but without the wavelengths that are less effective in endogenous vitamin D production. Exposure of individuals with varying skin types to these lights will enable us to observe the effect of artificial UVR exposure in creating vitamin D in individuals with varying shades of skin color. The benefit of this lamp will allow individuals who live in northern locations or individuals with malabsorption problems to create vitamin D.

Solius previously has completed two human clinical trials. The first study was a pilot feasibility study aimed to validate if the Solius Photobiological System efficiently stimulated the endogenous vitamin D process. The second study was a randomized non-inferiority study comparing the SOLIUS device to oral vitamin D supplements.

In a prospective cohort study (QR-TRP-002), six healthy adults with Fitzpatrick skin types I, II, and III were exposed to a 0.75 minimal erythemal dose (MED) of UVB radiation to approximately 75% of their body surface area once per week for 4 weeks. The individual dose was determined with Fitzpatrick skin typing, followed by exposure of the underneath of one forearm to 10 successively increasing durations of exposure to UVB. The subjects had a significant increase in mean 25(OH)D from 22.8  $\pm$  13.9 ng/ml to 27.2  $\pm$  12.0 ng/ml (P<0.05), representing a 19% increase over baseline after 4 weekly UVB exposures. No adverse events occurred.

Another study was performed on military personnel. Military personnel are at high risk for low vitamin D status which is common in individuals who regularly perform extreme physical exertion, particularly in combination with periods of psychological stress, inadequate nutrition, and sleep disruption. A total of 98 participants enrolled in the study; 10 (10.2%) either dropped out or were removed after enrollment. The final sample included 45 participants in the supplement and 43 in the phototherapy group. There were no between group differences noted based on age or gender distribution (P=0.06). There were also no between group differences observed with respect to race / ethnicity, Fitzpatrick skin type, birth location with respect to 37th parallel, prior diagnoses of vitamin D deficiency, vitamin D supplementation history, stress fractures, or family history of bone disorders, and total number of hours per week of sun exposure, with P > 0.05 for these groups.

The median serum 25(OH)D levels at baseline for the supplement and phototherapy were 25.0 ng/mL (IQR 21.0–32.0) and 28.0 ng/mL (IQR 22.0–35.0), respectively. By month three, the phototherapy group showed significantly higher levels of serum 25(OH)D than the supplement group (P=0.01, ŋ2=0.08) with a median level of 25.5 ng/mL (IQR 21.0–29.8) compared to a median level of 30.0 ng/mL (IQR 25.8-37.0) for the phototherapy group. By the four-month follow up the two groups again showed a slight difference in serum 25(OH)D levels with higher levels in the phototherapy group (P=0.04, ŋ2=0.05). At this timepoint the supplement group had decreased from baseline to median levels of 21.0 ng/mL (IQR 17.0-30.0) and phototherapy returned to baseline (median 27.0 ng/mL, IQR 22.0-32.5) (see supplementary documents).

With suboptimal intake of key nutrients like calcium and vitamin D, historically low compliance with taking pills, and low sun exposure, limited potential to optimize serum 25(OH)D continues to pose a threat to physical and mental health, disease prevention, and resilience so critical to individual wellness and readiness. At a time when self-care measures are highly valued for health promotion, programmed UVB photobiologic therapy, available as a kiosk in the community, appears to be a safe, efficacious alternative to oral vitamin D supplementation.

As discussed above, there is an ever growing need to improve the vitamin D status of the global population. Many individuals who live above 37° latitude and/or have malabsorption problems will greatly benefit from an artificial light source to combat their increased risk for vitamin D deficiency. The purpose of this study is to observe the effects of exposure of individuals of varying shades of skin color to Solius light source. The findings from the study have enormous health implications as it could be a potential treatment plan for many people battling vitamin D deficiency.

This study will be conducted in compliance with the protocol, applicable regulatory requirements, and BMC/BU Medical Campus Human Research Protection policies and procedures.

# 3.2 Rationale and Purpose

The FDA has required that Solius complete a clinical study with statistical significance to demonstrate that the Solius device can safely treat vitamin D insufficiency or deficiency.

## 4 Objectives

## 4.1 Study endpoint

The endpoint is to improve vitamin D status in the treatment group compared to sham controls. We expect at least 70% of vitamin D deficient/insufficient subjects in the treatment group to convert to insufficient/ sufficient. Also, because of seasonal variations and other confounders, we expect maximum 30% of subject convert to insufficient/sufficient in sham control group.

#### Study Outcome Measures

Improvement of serum concentrations of 25(OH)D will be measured by 25(OH)D analysis at baseline, each month and the end of the study. Serum 25(OH)D levels will be determined using the Liquid Chromatography with tandem mass spectrometry (LC/MS/MS) method.

## 4.1.1 Endpoint Measures

- 1. At each visit, the subjects will be asked to report any adverse events and any skin changes. These adverse events will be tabulated and reported at the study completion.
- 2. Blood samples will be obtained all subjects (case and control) monthly at various stages throughout the 5-week titration and 16-week intervention. Blood samples will be obtained once a week for 4 weeks after the 16-week intervention. Baseline samples will be obtained immediately preceding the first UVB exposure. Blood samples will be sent to the Quest Diagnostics for determining the serum 25(OH)D levels. An additional tube of blood will be collected for future study at week 1, week 5, week 13, week 21 and week 25.

# 5 Study Design

This is a double-blinded sham control clinical trial seeking to determine the safety and efficacy of the Solius Photobiologic System in increasing the serum concentrations of 25(OH)D in a vitamin D deficient/insufficient adult population. We will make our best effort to recruit individuals with all Fitzpatrick skin types as requested by the FDA. The study will be conducted at Boston University after it is approved by Boston University's Institutional Review Board.

	Table 1: Fitzpatrick Skin Types												
Skin type	Typical Features	Tanning ability											
ł	Pale white skin, blue/green eyes, blond/red hair	Always burns, does not tan											
11	Fair skin, blue eyes	Burns easily, tans poorly											
111	Darker white skin	Tans after initial burn											
IV	Light brown skin	Burns minimally, tans easily											
V	Brown skin	Rarely burns, tans darkly easily											
VI	Dark brown or black skin	Never burns, always tans darkly											

Each subject will be categorized into one of 6 Fitzpatrick skin types, type I, II III, IV and skin type V or VI. Skin types V and VI will be combined to represent the group with the darkest skin tone for subgroup analysis.

A total of 80 adult subjects with 5 skin types groups (I, II, III, IV and V/VI) will be enrolled for vitamin D deficiency/ insufficiency screening. The screening test for 25(OH)D will be performed by the Boston Medical Center's clinical laboratory for local Quest diagnostic laboratory which is able to perform the test within 24 hours. We expect at least 80% of the population in the Boston area has a level of 25(OH)D

below 30 ng/ml. Thus, we expect to enroll approximately 100 subjects with different group skin types to enroll 80 vitamin D deficient or insufficient subjects in this study. The research coordinator will be responsible for randomization and allocation. Thus, the study will be blinded to other members of the research team. Solius and the PI will have no contact with the participants. Subjects will be selected to or not to receive the UVB intervention (40 subjects in the treatment group and 40 subjects in the control group) (Figure 1). Two study groups will be matched by age, sex, BMI, and skin type by stratified randomization.

The device will have a strip of blue/purple colored LEDs installed inside the device. For users that are defined in the treatment group, both UVB lamps and blue/purple colored LEDs will turn on during the treatment. For users that are defined in the control group, they will go through the same pre-treatment workflow. However, when the user hits start treatment program in the device, only the blue/purple LEDs will turn on instead of the UV lamps, which emit radiation that is not visible to the naked eye.

Blood samples that will be obtained at the screening visit will be sent to either BMC's clinical laboratory or a local Quest laboratory for a 24 hour turnaround to determine eligibility of each participant. All blood samples collected monthly during the intervention and weekly after the intervention will be sent to Quest Diagnostics for measurement of serum concentrations of 25(OH)D by liquid chromatography with tandem mass spectrometry analysis as requested as requested by the FDA. The study design is summarized in Figure 1 and Table 2. As shown in the Table 2, blood samples will be collected at the screening visit, during the intervention period (week 1, week 5, week 9, week 13, week 17 and week 21). As requested by the FDA, we will also obtain blood sample after the intervention (week 22 – 25). We will collect an additional tube of blood for future study at week 1, week 5, week 13, week 21 and week 25.

Figure 1. Summary of protocol: Evaluating the effect of the Solius Photobiologic System in improving vitamin status in adults

Activity	Screening		Т	itratio	n									Interv	ention							
		Wk	Wk	Wk	Wk	Wk	Wk	Wk	Wk	Wk	Wk	Wk	Wk	Wk	Wk	Wk	Wk	Wk	Wk	Wk	Wk	Wk
		1	2	3	4	5	6	7	8	9	10	11	12	13	14	15	16	17	18	19	20	21
Informed	х																					
Consent																						1
Inclusion/Exc	х																					
lusion																						1
Medical	х																					
History																						1
Demographi	х																					
cs/																						1
Skin typing																						1
UVB		Х	Х	Х	Х	Х	Х	Х	Х	Х	Х	Х	Х	Х	Х	Х	Х	Х	Х	Х	Х	Х
Exposure/sh																						1
am exposure																						
25(OH)D	х	Х				Х				Х				Х				Х				Х
Additional						Х								Х								Х
blood																						1
Sun	Х					Х				Х				Х				Х				Х
exposure/																						1
Vit. D food																						1
checklist																						
Concomitant	Х	Х	Х	Х	Х	Х	х	Х	Х	Х	Х	Х	х	Х	Х	Х	х	Х	Х	Х	Х	Х
Medications																						
Adverse		Х	Х	Х	Х	Х	х	Х	Х	Х	Х	Х	х	Х	Х	Х	х	Х	Х	Х	Х	Х
Events																						

Activity	Po	ost-inte	erventi	on
	Wk	Wk	Wk	Wk
	22	23	24	25
Informed				
Consent				
Inclusion/Exc				
lusion				
Medical				
History				
Demographi				
cs/				
Skin typing				
UVB				
Exposure/sh				
am exposure				
25(OH)D	Х	Х	Х	Х
Sun				Х
exposure/				
Vit. D food				
checklist				
Concomitant	Х	Х	Х	Х
Medications				
Adverse	Х	Х	Х	Х
Events				

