## 7 Study Subject Selection

## 7.1 Subject Inclusion Criteria

In order to be eligible to participate in this study, an individual must meet all of the following criteria:

- 1. Age at least 22 years old
- 2. Male or Female
- 3. Skin Type I-VI
- 4. Women of child bearing potential must be on birth control and not pregnant based on a negative pregnancy test at baseline.
- 5. Ability and Willingness to give informed consent and comply to protocol requirements
- 6. Serum total 25(OH)D < 30 ng/mL

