# 12 Statistical Plan

The endpoint is the difference in vitamin D insufficiency/sufficiency prevalence between the treatment and the control group use at 16 weeks of follow-up. The subject will have at least one serum 25(OH)D

evaluation within 16 weeks, and at least one phototherapy session in the 16 weeks follow up. The protocol includes a sample size calculation, which allowed for a loss to follow-up of 15%.

Statistical analysis will be performed using SPSS Statistics, version 25 (IBM Corporation). Age, sex, BMI, and Fitzpatrick skin type will be matched in two study groups. Two-sided P < .05 will be considered significant. All models will be developed according to the intention-to-treat principle. A supportive analysis will also be conducted on the per-protocol (PP) population.

The biological and clinical characteristics at enrolment will be presented, and all variables for the participants in the treatment and control groups will be compared at each follow-up using Fisher's exact test for categorical variables and a Mann–Whitney *U* test for continuous variables. For intergroup differences, 95% CIs will be also calculated. The endpoint, the proportion of subjects converting from vitamin D deficiency/insufficiency to vitamin D insufficiency/sufficiency at 16 weeks will be compared between groups using Fisher's exact test and logistic regression adjusting for skin types. Secondary analysis will be involved a comparison of changing in serum levels of 25(OH)D between groups using a Mann–Whitney *U* test and linear regression adjusting for skin types. A linear mixed model will be used to examine the relationship between phototherapy and serum 25(OH)D3 at different time points, adjusting for the baseline values and correlation of outcomes within individuals and season.

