## 12.2 Sample Size Determination

The endpoint of this study is to compare the improvement of vitamin D status between treatment group and the controls. A previous study by Chandra et al. demonstrated the increase in the mean serum 25(OH)D in subjects with malabsorption syndrome receiving UV therapy from 21± 3 ng/mL to 27±4 ng/mL after 8 weeks (13). We would expect that to increase the serum 25(OH)D level by 10 ng/mL (SD=5ng/ml), after 16 weeks based on a previous study (13) as well as an earlier pilot study that was completed by Solius.

The endpoint is to improve vitamin D status in the treatment group compared to sham controls. We expect that the serum levels of 25(OH)D will increase more than 10 ng/ml (SD=5ng/ml) after 16 weeks of intervention in the treatment group compared to controls. Subjects converted from vitamin D deficient/insufficient to insufficient/sufficient is considered a minimum clinical important difference (MCID). We expect at least 70% of vitamin D deficient/insufficient subjects in the treatment group to convert to insufficient/ sufficient. Also, because of seasonal variations and other confounders, we expect maximum 30% of subject convert to insufficient/sufficient in sham control. With the desired power of 80% and significance level ( $\alpha$ ) of 0.01, the sample size in each group is 35.

Approximately 100 adult subjects with 5 skin types group (I, II, III, IV and V/VI) will be enrolled for vitamin D deficiency/ insufficiency screening. We expect that at least 80% of the population in the

Boston area has a level of 25(OH)D below 30 ng/ml. Thus, we will enroll 100 subjects with different skin types to enroll 80 vitamin D deficient or insufficient subjects in this study. We plan to match treatment and control group for age, sex, BMI and skin type by stratified random sampling (40 subjects in each group). In our experience, the rate of screen failure and subject dropout is 10-15%. Then, we expect to have at least 35 subjects per each group.

Parameters	Value
Conversion of the subjects from vitamin D deficient to vitamin D	70%
insufficient/sufficient or vitamin D insufficient to vitamin D sufficient in the	
treatment group after 16 weeks (P1)	
Conversion of the subjects from vitamin D deficient to vitamin D	30%
insufficient/sufficient or vitamin D insufficient to vitamin D sufficient in the control	
group after 16 weeks (P2)	
Significant level	0.01
Power	80%

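### If age, sex, BMI and five skin-type groups are crossed, 80 subjects fall into at least 40 strata, and neither the stated matching nor the 40:40 split is guaranteed

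*Combined protocol and SAP*

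**What the plan says.** Section 5 says "Two study groups will be matched by age, sex, BMI, and skin type by stratified randomization", with "40 subjects in the treatment group and 40 subjects in the control group". Section 12 presents this as a settled feature of the data: "Age, sex, BMI, and Fitzpatrick skin type will be matched in two study groups". Section 12.2 says the plan is to "match treatment and control group for age, sex, BMI and skin type by stratified random sampling", again at 40 per group. Section 12.2 speaks of sampling where Section 5 speaks of randomisation.

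On the levels of the factors the document says little:

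- **Skin type:** five groups (I, II, III, IV, V/VI) are used for screening and recruitment. Section 5 explains the merging of the last two by saying "Skin types V and VI will be combined to represent the group with the darkest skin tone for subgroup analysis". It does not say that the same five groups define the randomisation strata.
- **Sex:** two levels (Section 7.1).
- **Age:** only a lower limit, "Age at least 22 years old" (Section 7.1). No classes.
- **BMI:** no classes.

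The document does not say whether the four factors are crossed. It gives no block size, no method for producing the list and no mention of minimisation. In Section 12 the primary logistic regression and the secondary linear regression adjust for skin type only. The linear mixed model lists baseline value, within-subject correlation and season.

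**The concern.** Stratified randomisation balances the arms only in so far as strata fill their blocks. Four crossed factors in 80 subjects leave many strata with no subject, one subject or an odd number, and every incomplete block can add to imbalance, both overall and within each factor.

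Skin type is the factor with most at stake. It sets the range of starting and maximum doses in titration (Sections 6.1 and 8) and the sham exposure time (Section 8). It is the only adjustment factor in the primary model, it is named for subgroup analysis in Section 5, and Section 12.1 expects the greatest response in types I and II. Sharing the stratification with age, sex and BMI gives skin type worse balance than it would have alone. Age, sex and BMI are named as matching factors but appear in none of the models, so any chance imbalance in them is left unadjusted.

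**Working it through.** **The plan's own figure.** The document states no number of strata. Its sample size comes from Section 12.2 (70% against 30%, alpha 0.01 two-sided, power 80%):

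N = (2.58 × √0.5 + 0.84 × √0.42)² / 0.4² = (1.824 + 0.544)² / 0.16 = 35.07.

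This reproduces the stated 35 per group (unrounded normal quantiles give 36). The plan recruits 40 per group.

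**Number of strata.** From the document: 80 subjects, two sexes, five skin-type groups. Assumed: full crossing, and two classes each for age and BMI as the minimum.

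- 5 × 2 × 2 × 2 = 40 strata; 80 / 40 = 2.0 subjects per stratum.
- With three classes each for age and BMI: 5 × 2 × 3 × 3 = 90 strata; 80 / 90 = 0.9.

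With subjects spread evenly over 40 strata, the expected number of empty strata is 40 × (39/40)^80 = 5.3. The expected number with one subject is 40 × 80 × (1/40) × (39/40)^79 = 10.8. About 20 strata hold an odd number.

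**Balance.** Simulated allocation of 80 subjects, factor levels evenly spread (assumed), at least 4,000 runs per scheme. Percentages are approximate.

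| Scheme | Exactly 40:40 | Arms differ by 6 or more | Some skin group off by 4 or more |
|---|---|---|---|
| 40 strata, blocks of 2 | 18% | 26% | 32% |
| 40 strata, blocks of 4 | 14% | 40% | 64% |
| 40 strata, blocks of 6 | 10% | 49% | 79% |
| 90 strata, blocks of 4 | 10% | 50% | 84% |
| Skin type by sex, blocks of 4 | 28% | 8% | 1% |
| Skin type only, blocks of 4 | 39% | 1% | 0% |
| Simple randomisation | 9% | 58% | 92% |

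The 0% for skin type only is structural: with blocks of 4, an incomplete block leaves a difference of at most 2 within a skin group. An uneven skin mix (assumed 5/20/30/25/20%) changes little: with 40 strata, exactly 40:40 occurs in 18% of runs with blocks of 2 and 14% with blocks of 4.

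**Consequence for power.** Normal approximation for two proportions, 70% against 30%, alpha 0.01 two-sided:

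power = Φ{[0.4 − 2.576 × √(p̄q̄(1/n₁ + 1/n₂))] / √(p₁q₁/n₁ + p₂q₂/n₂)}.

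At 40:40 this is Φ[(0.4 − 2.576 × 0.1118) / 0.1025] = Φ(1.09) = 86.3%. The same formula gives 86.2% at 38:42, 85.9% at 36:44 and 85.4% at 34:46. With 40 strata, 95% of splits lie within 36:44 for blocks of 2, 34:46 for blocks of 4 and 33:47 for blocks of 6. Even 30:50 keeps 83.7%.

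**Consequence within a skin group.** A difference of 4 in 16 is 10:6 instead of 8:8. With equal variances the variance ratio is (1/10 + 1/6) / (1/8 + 1/8) = 1.07, about 3% on the standard error.

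**Room for covariates in the primary model.** Expected conversions are 40 × 0.7 + 40 × 0.3 = 40. Arm (1), skin type (4), age, sex and BMI (3) make 8 parameters, so 5 events per parameter. At 35 per arm it is 35 / 8 = 4.4.

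**The case against.** The strongest reply is that the 40 strata are not in the document. Crossing, cut-points and block size are all assumed, and the five skin groups are tied to recruitment and subgroup analysis, not expressly to the strata. That stands, and the point is conditional on it. It is nevertheless the ordinary meaning of stratified randomisation on four factors, and 40 is the lowest count on that reading with five skin groups.

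A reader might infer that the scheme delivers no balance and is simple randomisation in effect. The figures do not support this. With 40 strata and blocks of 2, the split is within 38:42 in 74% of runs and within 36:44 in 96%. The standard deviation of an arm's size is 2.2, 3.0 and 3.5 for blocks of 2, 4 and 6, against 4.5 for simple randomisation. Some benefit remains in every blocked version and shrinks as blocks grow.

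A reader might also infer a material loss of power or precision. There is none of note: under one point for splits to 34:46, and about 3% on the standard error in a 10:6 skin group. A subgroup of about eight per arm is weak even when perfectly balanced, and Section 12 specifies no subgroup analysis. Skin-type adjustment in the logistic and linear regressions already deals with part of any imbalance, though Fisher's test is unadjusted.

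Nor does skin type fix the treated dose. Sections 6.1 and 8 describe individual titration, with skin type setting the starting and maximum values; only the sham exposure time follows skin type directly.

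What survives all this is the comparison: in every blocked version considered, skin-type balance is worse than with skin type as the only stratifier.

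**Conclusion.** The concern holds in conditional form. The plan presents matching on four factors and a 40:40 split as properties of the design, without the details that would produce them. If the factors are crossed, there are at least 40 strata for 80 subjects and neither property is guaranteed. Some skin group is off by 4 or more in roughly a third to four fifths of trials, depending on a block size that is not stated, against about none when skin type is the only stratifier. The practical damage is modest: poorer balance on the factor that matters most, and a claim of matching that the report could not support. Validity is not threatened and overall power is almost unchanged. The figures rest on full crossing, two classes each for age and BMI, five skin strata and an even spread of subjects.

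**What to change.** Before the first subject is randomised:

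1. Stratify by the five skin-type groups only, or by skin type and sex, using small permuted blocks from a concealed list. State the block scheme in a document not available to those who enrol or allocate. Blocks of 2 alone are best avoided: Section 9 lets the coordinator know the A/B code, so every second allocation in a stratum would be predictable. If balance on all four factors is truly wanted, use minimisation and state its factors and classes.
2. Replace 'matched' with 'stratified by skin type' in Sections 5, 12 and 12.2, and correct 'sampling' to 'randomisation' in 12.2.
3. Add age, sex and BMI as covariates in the secondary linear regression and the mixed model; the latter should also list skin type.
4. Keep the primary logistic model adjusted for skin type. Report the version with age, sex and BMI as a sensitivity analysis, because there are only about 40 events for 8 parameters.

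The cost is a new list and some wording. Balance on age and BMI then rests on chance plus adjustment. With blocks of 4 little is given up: the mean imbalance within an age class is about 3.7 subjects, against 3.2 under full crossing. More would be given up relative to full crossing with blocks of 2.
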